Hypothesis 2: We will predict that the effects of rTMS will dissipate over 3 months following-up time in some smokers. We also will predict that the effects of rTMS will last more than 3 months in other smokers. The following-up data will provide the best fit of the relapse-time data relative to a variety of parametric alternatives.

Aim 3: To demonstrate whether the active rTMS and sham groups differ significantly in side effect profiles, and whether the frequency and severity of side effects decreases over the course of treatment.

Hypothesis 3: The frequency and severity of side effects will not differ between the active rTMS and sham groups, and decreases over the course of the treatment, suggesting adaptation or tolerance.

RESEARCH STRATEGY

1. Significance

Nicotine dependence remains a significant public health concern. In 2011, the World Health Organization (WHO) reported that tobacco use continues to be the leading global cause of preventable death, killing nearly 6 million people and causing hundreds of billions of dollars of economic damage worldwide each year ²⁵. In the United States, cigarette smoking is the leading preventable cause of mortality accounting for approximately 1 out of every 5 deaths ¹. On average, smokers die 13 to 14 years earlier than nonsmokers ²⁶. Cigarette smoking is the most common form of tobacco use and 45.3 million persons (19.3% of the population) are current cigarette smokers. Additionally the estimates for average annual smoking-attributable productivity losses are \$96.8 billion and the total economic burden of smoking is approximately \$193 billion per year ²⁷.

The 2010 National Health Interview Survey revealed that approximately 70% of current smokers want to quit and 41% have tried to quit, however few of these attempts were successful with only 4.7% of current smokers able to stop smoking for at least three months ². Despite the availability of therapeutic options for smoking cessation, only 6% of the 35 million smokers who report wanting to quit each year are successful in doing so for more than a month ^{8, 9}. **Clearly, there is room for improvement in smoking cessation.**

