- 9) Tobacco diary: This is a daily diary of all tobacco products consumed in the period between visits, including cigarettes. Participants will maintain a daily tobacco diary, which will be collected at each visit. We have piloted a similar diary in our previous studies. Time-Line Follow-Back is not designed for daily prospective monitoring and hence a tobacco diary will be used.
- 10) Other drug diary: If participant uses marijuana and other drugs, diaries to document other substance use will be provided.
- 11) Modified Cigarette Evaluation Questionnaire- mCEQ: This questionnaire assesses the reinforcing effects of smoking.
- 12) Self Assessment Manikin (SAM) ⁸⁴. SAM is a graphical picture-oriented instrument that can directly assess the pleasure, arousal, and dominance experienced in response to a cue exposure. SAM ranges from a smiling, happy figure to a frowning, unhappy figure when representing the pleasure dimension, and from an excited, wide-eyed figure to a relaxed, sleepy figure for the arousal dimension. The dominance dimension represents changes in control with changes in the size of SAM: a large figure indicates maximum control in the situation. The participants will rate their subjective "happy", "excited", and "control" states.

Table 1. Schedule for data collection

Assessments	Baseline	The 1 st Week TMS	The 2 nd Week TMS	The 1st Follow- up Visit One Week After TMS	The 2 nd Follow- up Visit One Month After TMS	Follow-up Phone Three Months After TMS
Demographic	Х					
Medical history	Х					
Physical exam	Х					
Neuro exam	Х					
MINI	Х					
Psychiatric	х					
evaluation						
Tobacco history	Х					_
FTND	Х	Х	X	Х	Х	Х

QSU-B	Х	Х	Х	Х	Х	
BDI	Х					
MNWS-R	Х					
CO	Х	x daily pre	x daily pre	Х	Х	
Craving rating panel	Х	x daily pre post	x daily pre post			
Tobacco diary	Х	Х	Х	Х	Х	Х
Adverse Events	Х	x daily pre post	x daily pre post	Х	Х	Х
Drug diary	Х					
mCEQ	Х	Х	X	X	Х	
Hematology	Х					
Routine urinalysis	Х					
Urine cotinine	Х	Х	X	X	Х	
Pregnancy test	X					
Urine drug	Х					
MRI scan	Х		TMS Day 10			
Best guess	Х		Х			

- **5. Randomization.** Subjects will be randomized to either sham rTMS over DLPFC or real rTMS over DLPFC with Data Coordination Unit (DCU) at MUSC. Briefly, the subject will be assigned a study number and will then be assigned either a sham or active TMS smart card. An Active Smart Card will only allow TMS treatment with the active TMS head coil. A Sham Smart Card will only work with the sham TMS coil.

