- 4). Weekly Assessments: At the end of the 5th and the 10th treatment and 1 week and 1 month follow-up visits, subjects will complete FTND, MNWS-R, Tobacco diary, mCEQ and adverse events.
- 5). At the end of the experiment, subjects will be asked what treatment (active or sham) he/she believes was completed.
- **9. Follow-up (Specific Aim 2).** The treatment period of the study will conclude on the end of two weeks. Participants will then enter the follow-up phase of the study. The two follow-up visits will be scheduled one 1 week and 1 month after the 10th rTMS session. Data will include craving ratings, tobacco diary, CO, QSU-B and FTND. We will conduct a follow-up phone survey of participants 3 months after the 10th treatment. Cigarette consumption will be evaluated by asking: 'How many cigarettes do you now smoke on an average day?'. Craving will be assessed by asking: 'How much do you want to smoke a cigarette right now on a scale from 1 to 10?' and "When was your last cigarette?'. Nicotine dependence will be assessed by the FTND.
- 10. Data Analyses. All data will be analyzed in consultation with Data Coordination Unit (DCU) at MUSC. Quantitative measures of nicotine dependence: Craving rating panel, Tobacco diary, CO, QSU-B and FTND. Side effects: Following standard procedures, frequency and severity measures of side effects will be constructed from the clinical measures. Significance testing: All tests will be two-sided, performed at significance α =0.05, except where noted. The statistical approach will use an ANOVA for each outcome variable. Some data may be longitudinal as well as cross-sectional and we will include random effects to account for within-subject correlation.

Power Analysis. The primary efficacy of rTMS for this study will be the abstinence rate and the number of cigarettes smoked per day at the end of treatment. One previous study of rTMS reported that 10 sessions of rTMS significantly reduced the number of cigarettes per day by the 10^{th} treatment ($18.11 \pm 2.61 \text{ vs.} 10.71 \pm 2.19$) ¹⁹. A power analysis was conducted based upon this two group design, a power of 0.8, and an alpha level of 0.05; a significant difference is anticipated with 18 subjects in each group. The attrition rate in the above mentioned study was 8%. The attrition rate for our previous study was 12% ³¹. According to the attrition

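### The 3-month phone script does not ask when smoking resumed, so the relapse times that Hypothesis 2 needs have no secure source after the 1-month visit

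*Combined protocol and SAP*

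**What the plan says.** - **Specific Aims, Hypothesis 2:** "The following-up data will provide the best fit of the relapse-time data relative to a variety of parametric alternatives".
- **Section 9, Follow-up:** "The two follow-up visits will be scheduled one 1 week and 1 month after the 10th rTMS session", and then "We will conduct a follow-up phone survey of participants 3 months after the 10th treatment". The call's questions are "How many cigarettes do you now smoke on an average day", a 1-to-10 craving rating, "When was your last cigarette" and the FTND. The last-cigarette question is grouped with the craving item.
- **Section 4, item 9 (Tobacco diary):** "This is a daily diary of all tobacco products consumed in the period between visits, including cigarettes". On its return: "Participants will maintain a daily tobacco diary, which will be collected at each visit".
- **Table 1:** the tobacco diary is marked in all six columns, including "Follow-up Phone Three Months After TMS".
- **Section 8, item 4 (Weekly Assessments):** the diary is listed after the 5th and 10th treatments and at the 1-week and 1-month visits, with no 3-month entry.
- **Section 10, Data Analyses:** ANOVA with random effects. There is no definition of relapse, no time origin, no time-to-event model and no censoring rule.

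**The concern.** A relapse time is the date on which a person who had stopped starts smoking again. A last-cigarette date measures time since the most recent smoking. The two agree only for someone who lapsed and stopped again. Someone who resumed on day 35 and someone who resumed on day 80, both smoking daily, give the same answer at the call.

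The call is the only contact for about two of the three months that Aim 2 covers. If the diary does not reach the study for that period, nothing collected says when in those two months smoking resumed. How long the benefit lasts, and which parametric form fits best, would then rest on the first month and on a status at month 3. The Power Analysis section also says the follow-up data will feed power calculations for later studies, so an error in duration could carry forward.

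**Working it through.** The plan states no relapse rate or fitted duration, so there is no figure of its own to reproduce. The check has two parts.

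**1. Sources of a date between month 1 and month 3**

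- *Call, cigarettes per day:* current level, undated.
- *Call, craving rating and FTND:* current state, undated.
- *Call, last cigarette:* dated, but for a current smoker the date is about that of the call.
- *Diary:* would date the first cigarette. Table 1 schedules it for the call. Section 4 collects it at visits, section 8 lists it up to the 1-month visit, and section 9 names it before describing the call and not among the call's questions. No route for returning a diary at a phone contact is described.
- *Payments (Human Subjects, section 5):* 70 + 10 × 40 + 25 + 2 × 50 = 595 dollars, the stated total. No later paid visit is hidden in it.

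The call therefore yields no date of resumption for a current smoker, and the diary's availability is contradictory.

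**2. What would follow if the last-cigarette date were used as the relapse date**

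Assumptions, none from the plan: exponential relapse times with median *m* from the end of treatment; relapses up to day 30 dated exactly; call on day 90; everyone who relapsed after day 30 is smoking daily at the call.

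- Share relapsing in days 30–90: p = 2^(−30/m) − 2^(−90/m)
- Share relapsing by day 90: F = 1 − 2^(−90/m)
- Mean delay in their date: d = 60 − [m/ln 2 − 60q/(1 − q)], with q = 2^(−60/m)
- The fitted exponential hazard is events divided by person-time. Misdating leaves events unchanged and adds p × d days per participant, so the fitted median is m + ln 2 × p × d / F.

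For m = 60: p = 0.7071 − 0.3536 = 0.3536; F = 0.6464; d = 60 − (86.56 − 60) = 33.4; fitted median = 60 + 0.693 × 0.3536 × 33.4 / 0.6464 = 72.7 days.

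| Assumed median (days) | p | d (days) | F | Fitted median, dated to call |
|---|---|---|---|---|
| 15 | 0.234 | 42.4 | 0.984 | 22.0 |
| 30 | 0.375 | 36.7 | 0.875 | 40.9 |
| 60 | 0.354 | 33.4 | 0.646 | 72.7 |

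Maximum-likelihood fits to 4,000 simulated participants agree (days, in the same order):

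- dated to the call: 21.9, 40.6, 72.8
- exact dates: 14.9, 29.6, 60.3
- interval-censored between day 30 and day 90: 15.0, 29.5, 60.2

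A Weibull model fitted to the call-dated data gave shapes of 0.82, 0.95 and 1.11 where the truth is 1, so the choice among parametric forms is disturbed as well. With exact or interval-censored data the shape was 1.01 to 1.02.

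**The case against.** A reader might infer that every relapse after the 1-month visit will be dated to the day of the call, and that the relapse-time fit is therefore wrong. The documents do not support that.

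- Nothing says the last-cigarette answer becomes the relapse date; it is a craving-block question.
- Table 1 does schedule the diary for the 3-month contact, and section 4 chooses a diary precisely because it is daily and prospective. If returned, it would date the first cigarette.
- Someone who lapsed once and stopped again would report the true date.
- No time-to-event model is specified, so no particular fit can be called wrong. The same contact data handled as interval-censored show almost no bias above.
- Participants who never stopped can be identified at the 1-week and 1-month visits from the diary, CO and cotinine.
- Few participants may be at risk. The Specific Aims cite 6% of smokers who want to quit succeeding for more than a month. Applied to 42 as an assumption, that is 0.06 × 42 ≈ 2.5 people; at an assumed 25% it is about 10. Sampling error could then exceed the bias shown.
- Aim 2 also names cigarettes per day and nicotine dependence, which the call does measure.

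All of this stands against the stronger reading. What it leaves is that the script omits the question Hypothesis 2 depends on, and that one table mark without a collection route does not secure the dates. Interval censoring removes the bias but leaves a single interval of about 60 days, with no information on timing inside it, so it helps little in choosing among parametric forms.

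**Conclusion.** The point holds as a gap in data collection and an inconsistency between passages, not as a demonstrated error in an analysis. As written, the call cannot date relapse in anyone smoking again, and the diary cannot be relied on to do so until Table 1 is reconciled with sections 4, 8 and 9.

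The overstatement of the fitted median (7.0/15 = 47%, 10.9/30 = 36%, 12.7/60 = 21%) is conditional on using the last-cigarette date as the relapse date, on exponential relapse, and on the assumed medians. It is a large-sample illustration and not a forecast for 42 participants. The end-of-treatment primary outcome is untouched. The change is still worth making before the calls begin, because the missing date cannot be recovered reliably afterwards.

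**What to change.** 1. In the section 9 call, ask participants who had stopped smoking for the date of their first cigarette after stopping and the date they returned to regular smoking, prompted by the date of the 1-month visit.
2. Keep the last-cigarette question for current abstinence only, and say so.
3. State how the month 1–3 diary is returned (for example by post, or read out during the call), or remove the mark from the phone column of Table 1.
4. In section 10, define relapse, its time origin and the source of its date. Where no date is available, treat relapse as interval-censored between the last contact at which the participant was abstinent and the call.

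The cost is one or two questions in a call already planned and a standard likelihood in the same parametric models. Recalled dates carry some error; a participant who cannot give a date falls under the interval-censoring rule.

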The baseline evaluation will occur on the same day if the subjects meet the inclusion/exclusion criteria and sign the consent form.

- 1) Demographic Data: Basic demographic information including age, gender, race, and social history will be collected.
- 2) Mini International Neuropsychiatric Interview (MINI) ⁸⁰: This is a well-standardized structured instrument used to provide quick and accurate DSM-IV psychiatric diagnoses. The MINI will be used to confirm the inclusionary/exclusionary diagnoses in the participants.
- 3) Tobacco Use History: Detailed history of current and past tobacco use will be obtained, including cigarette smoking. The questions addressed will include the amount, frequency, duration of smoking, preferred brand, reasons for smoking, smokeless tobacco, family history, etc.
- 4) Fagerstrom Test for Nicotine Dependence (FTND)⁸¹: This is a self-rating questionnaire for nicotine dependence.
- 5) Questionnaire of Smoking Urges- Brief (QSU-B) 82: This is a 10-item self-rating questionnaire for assessment of craving. The questionnaire will be used to track the level of craving during the study. In addition to a total score, the QSU provides scores on two factors: 1) hedonic craving, in anticipation of positive effects, and 2) craving in anticipation of withdrawal relief.
- 6) Beck Depression Inventory II (BDI) ⁸³: BDI is a 21-item self-rating scale to assess symptoms of major depression. We will monitor depressive symptoms during the study due to strong association between smoking and depressive disorders.
- 7) Minnesota Withdrawal Scale Revised (MNWS-R) ⁴: MNWS-R is a DSM-IV based instrument to assess symptoms of nicotine withdrawal.
- 8) Biomarkers: Urine cotinine levels will be used as biomarkers for cigarette smoking. We will use a dipstick urine cotinine (NicAlert, Nymox Pharmaceuticals). NicAlert is a semi-quantitative enzyme linked immunoassay (Elisa test) dipstick measure of salivary or urine cotinine with ranges of 0 10, 10 30, 30 100 ng/ml, etc. The NicAlert dipstick will be done at each study visit. We will also use carbon monoxide (CO) level in the expired air by a standard CO breathalyzer at each visit.

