- 3). Quality Assurance: The PI will have weekly meetings with the research assistants to discuss qualitative comments received during data collection and any problems in data collection. The statistician will periodically examine the database to look for irregularities. Initial data analyses will examine distributions of variable scores, and comparability of baseline characteristics across conditions in case analyses need to be adjusted for these. Confidentiality protections are outlined above.
- 4). Regulatory Issues: All unexpected Adverse Events (AEs) will be reported to the MUSC IRB and Committee on Human Research within 48-business hours. Serious AEs will be reported within 24-business hours. Follow-up of all unexpected and serious AEs will also be reported to these agencies.
- 5). Definition of AE and SAE: An AE is defined as any untoward medical occurrence in a study subject administered a pharmaceutical product that does not necessarily have a causal relationship with this treatment (ICH GCP). Any unwanted change, physically, psychologically or behaviorally, that occurs in a study participant during the course of the trial is an adverse event. A Serious Adverse Event (SAE) is defined as an adverse event that has one of the following outcomes: death, life-threatening, inpatient hospitalization or prolongation of existing hospitalization, persistent or significant disability/incapacity, a congenital anomaly/birth defect.
- 6). Documentation and Reporting: AEs/SAEs are documented and reported as per IRB requirements. Research staff will identify adverse events and obtain all available information to assess severity, seriousness, study relatedness, expectedness, outcome and the need for change or discontinuation in the study intervention. Adverse events are generally documented on AE Logs and AE Case Report Forms (CRFs). Additional relevant AE information if available will be documented in a progress note in the research record as appropriate to allow monitoring and evaluating of the AE. If the AE meets the definition for serious, appropriate SAE protocol specific reporting forms are completed and disseminated to the appropriate persons and within the designated timeframes as indicated above. For each AE/SAE recorded, the research staff will follow the AE/SAE until resolution, stabilization or until the participant is no longer in

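### The ANOVA names no baseline covariate and adjustment waits on an undefined comparability check, so the precision available from baseline values already collected is not secured

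*Combined protocol and SAP*

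**What the plan says.** Section 10 (Data Analyses, Significance testing) states: "The statistical approach will use an ANOVA for each outcome variable". For data that may be longitudinal it adds that "we will include random effects to account for within-subject correlation". It lists no fixed effects, does not say whether the response is an end value or a change, and gives baseline no role.

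The Power Analysis paragraph names as the primary efficacy measures "the abstinence rate and the number of cigarettes smoked per day at the end of treatment". From a cited difference of 18.11 ± 2.61 against 10.71 ± 2.19 cigarettes per day, it concludes that "a significant difference is anticipated with 18 subjects in each group".

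Adjustment is mentioned once, in the Data and Safety Monitoring Plan (item 3, Quality Assurance). Initial analyses will look at "comparability of baseline characteristics across conditions in case analyses need to be adjusted for these". No criterion, covariate list or model follows, and it is not said whether an outcome's own baseline value counts as a baseline characteristic.

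Table 1 schedules the craving rating panel, tobacco diary, CO, QSU-B and FTND at baseline. For cigarettes per day the baseline source is unclear. Section 4 says "The baseline evaluation will occur on the same day if the subjects meet the inclusion/exclusion criteria and sign the consent form". Its tobacco history is recalled ("The questions addressed will include the amount, frequency, duration of smoking"), while the diary is described differently: "This is a daily diary of all tobacco products consumed in the period between visits, including cigarettes". The number of diary days before the first session is not stated.

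**The concern.** In a randomized trial, adjusting a continuous outcome for its own baseline value removes the part of the outcome variance that baseline predicts. This works whether or not the arms happen to be balanced. A rule that adjusts only when imbalance is seen misses this, because randomization makes marked imbalance uncommon and the precision is available every time. With about 36 evaluable participants expected, precision is scarce.

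The wording also fits several analyses: end value only, end value adjusted for baseline, or change from baseline. These have different power and can give different p-values on the same data. Leaving the choice until the data are seen weakens whichever result is reported.

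**Working it through.** **Inputs from the protocol.** Two-sided alpha 0.05, power 0.80, 18 evaluable per group, 1:1 allocation, 12% attrition, and 18.11 ± 2.61 against 10.71 ± 2.19 (section 10, and section 1 of Experiment Approach). The correlation r between baseline and end value is not given, so it is varied from 0 to 0.7.

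**The plan's own figure.** The difference is 18.11 − 10.71 = 7.40. The ± values are not labelled.
- Read as SDs: pooled SD = √((2.61² + 2.19²)/2) = 2.41, and d = 7.40/2.41 = 3.07. About 3 per group would give 80% power by the t-test, so 18 does not follow.
- Read as standard errors: 18 per group follows by the t-test if the cited study had about 10 per group (SD = 2.41 × √10 = 7.62, d = 0.97). The protocol does not give that group size.
- The attrition step reproduces: 18/(1 − 0.12) = 20.5, so 21 per group and 42 in total.

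**Effect used below.** Solving for 80% power at 18 per group with a two-sided t-test gives d = 0.961, which for a difference of 7.40 implies an SD of 7.40/0.961 = 7.70. This is the effect implied by the plan's sample size, not one it states.

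**Formula.** Adjustment for baseline multiplies the residual variance by (1 − r²): 0.91 at r = 0.3, 0.75 at 0.5 and 0.51 at 0.7. The standard error of the treatment difference falls by 5%, 13% and 29%. Power from the noncentral t with 33 df is 83.5%, 89.8% and 97.5%. This is slightly optimistic because it ignores chance baseline imbalance, which the simulation includes.

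**Simulation.** Bivariate normal, equal variances, 18 per arm, d = 0.961, 40,000 trials per setting, Monte Carlo SE about 0.25 points or less:

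| r | End-value ANOVA | Always-adjusted ANCOVA | Unconstrained change contrast |
|---|---|---|---|
| 0 | 79.8% | 78.5% | 50.8% |
| 0.1 | 80.1% | 79.2% | 55.3% |
| 0.2 | 79.9% | 80.2% | 60.2% |
| 0.3 | 79.7% | 82.1% | 65.4% |
| 0.4 | 79.9% | 85.3% | 72.5% |
| 0.5 | 80.2% | 89.0% | 80.0% |
| 0.6 | 80.0% | 93.1% | 87.8% |
| 0.7 | 80.2% | 97.0% | 95.2% |

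ANCOVA type I error was 4.8–5.1%. Independent re-runs agree within simulation error.

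The change contrast also depends on the variance ratio. With the end SD at half the baseline SD and r = 0.5, its power is 36.3%, against 88.7% for ANCOVA.

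**Does the Quality Assurance check recover the gain?** The protocol gives no rule. If it means adjusting only when the arms differ at baseline with p < 0.05 (an assumption), power is 79.5, 79.6, 80.6 and 81.9% at r = 0, 0.3, 0.5 and 0.7. Type I error falls to 4.4% at r = 0.5 and 3.8% at r = 0.7. Almost none of the gain is recovered.

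**What the open choice could do.** As an upper bound, taking the better of end-value ANOVA and ANCOVA after seeing both gives type I error of 5.6–8.4% over r = 0 to 0.7. Taking the best of all three analyses gives 8.8–10.0%.

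**Non-normal cigarettes per day.** All inputs here are assumed: baseline 10 plus a gamma variable, end values gamma with zeros for abstainers, and the effect recalibrated to 80% end-value power. Three abstinence scenarios were run (sham/active 5/5%, 5/20%, 10/30%).

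| Observed r | Change in power from adjusting |
|---|---|
| 0 | about −1 point |
| 0.19–0.24 | 0 to +1 |
| 0.31–0.40 | +3 to +5 |
| 0.45–0.57 | +6 to +11 |
| 0.55–0.70 | +10 to +15 |

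**The case against.** The strongest reply is that no gain is demonstrated from the documents alone. Both d = 0.96 and r are assumptions, and if the ± values are SDs, power on cigarettes per day is near 100% either way. That stands, and it limits the claim to a range. It does not favour leaving adjustment out: the worst case for adjusting is about 1 point of power, and the SD reading cannot be squared with the plan's own 18 per group.

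Second, the plan does not say end value only. If baseline entered as a repeated measure, the right comparator at r = 0.7 would be the change contrast at 95.2%, leaving a gain of about 2 points, not 17. This is fair at high r. Below r = 0.5 the same reading makes the unadjusted plan worse, and the spread between readings shows why the model needs to be fixed.

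Third, craving is rated before and after every session, so its baseline is ambiguous, and pre-session ratings from session 2 onward may already reflect treatment. This is met by using the Baseline column of Table 1. It is also true that nothing in the documents anchors d or r for craving, CO, QSU-B or FTND, so the power figures are illustrative for those outcomes.

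Finally, this is an exploratory R21, the planned analysis is valid, and the comparability check looks at baseline data, not outcomes. These points limit the seriousness. They do not make the efficient analysis any harder to specify.

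**Conclusion.** The concern holds. The planned analysis is unbiased and keeps its type I error; what is missing is a commitment to use baseline values that are already scheduled. Under normality, d = 0.96 and 18 per group, always adjusting costs about 1 point of power at r = 0 to 0.1, gains nil to about 2 points at 0.2 to 0.3, and gains 9 to 17 points over an end-value ANOVA at 0.5 to 0.7. The benefit is worthwhile from a correlation of about 0.4 to 0.5 upwards. Confidence in the size is moderate, because r and d are not in the documents. Nothing is gained on cigarettes per day if the ± values are SDs. The conclusion does not extend to the abstinence rate, since entry requires at least 10 cigarettes per day and so everyone smokes at baseline. This should be changed, but it is a matter of efficiency and pre-specification, not validity.

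**What to change.** In section 10, for cigarettes per day, craving, CO, QSU-B and FTND, pre-specify an analysis that always adjusts for the outcome's own pre-treatment value (the Baseline column of Table 1, not later pre-session ratings), whatever the observed balance. Either form will do:

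- an ANCOVA, or a mixed model with baseline as a covariate; or
- a mixed model with baseline in the outcome vector and baseline means constrained equal across arms. This fits the existing random-effects sentence. With complete data at two time points it has the same maximum-likelihood treatment estimate as ANCOVA.

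Do not use an unconstrained group-by-time change test. Name the baseline source for cigarettes per day: recalled history, or a stated number of pre-treatment diary days. Make the Quality Assurance comparability check descriptive only. State the abstinence-rate analysis separately.

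The cost is two or three sentences of analysis wording, plus one for the baseline source. The analysis gives up one degree of freedom, which is about 1 point of power if the correlation is 0 to 0.1. The baseline assessments are already in Table 1. A recalled or very short baseline would lower the correlation, and with it the gain.

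### Section 10 prescribes ANOVA for every outcome and gives no binary method for abstinence, a yes/no primary outcome; at low quit rates the ANOVA may not be computable and its interval is unreliable

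*Combined protocol and SAP*

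**What the plan says.** Combined protocol and SAP, Experiment Approach, item 10 (Data Analyses): "The statistical approach will use an ANOVA for each outcome variable". The one extension is for repeated data, where "we will include random effects to account for within-subject correlation". On testing: "All tests will be two-sided, performed at significance α =0.05, except where noted".

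The Power Analysis paragraph that follows states: "The primary efficacy of rTMS for this study will be the abstinence rate and the number of cigarettes smoked per day", both at the end of treatment. The sample size is argued from cigarettes per day only: "a power of 0.8, and an alpha level of 0.05; a significant difference is anticipated with 18 subjects in each group", raised to 21 randomised per group for attrition.

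No logistic, exact or other binary method is given for abstinence, no abstinence rate is assumed, and abstinence is not defined. The quit rates in the protocol are background figures: 6% for more than a month among smokers wanting to quit (Specific Aims and Significance), and, in Significance, "only 4.7% of current smokers able to stop smoking for at least three months".

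**The concern.** ANOVA models an outcome as continuous with one common variance. For a yes/no outcome the variance depends on the rate, and when quitters are few it is estimated from almost no information. If nobody quits, it is zero and the F ratio is 0/0. The plan would then have no prescribed result for a primary outcome, and any interval printed with the ANOVA would be a point at zero.

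Two things are at stake. The first is whether the abstinence result can be interpreted at all in a small trial. The second is analyst discretion: if the stated method fails or is set aside after the data are seen, the choice of replacement test can decide which side of 0.05 a borderline result falls on.

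**Working it through.** **The plan's own figure.** It concerns cigarettes per day: 18.11 ± 2.61 versus 10.71 ± 2.19, difference 7.40, pooled spread √[(2.61² + 2.19²)/2] = 2.41. Reading ± as SD, n = 2 × [(1.96 + 0.84) × 2.41/7.40]² = 1.7, so 2 to 3 per group rather than 18. Reading ± as a standard error from about 10 per arm (an assumption; the arm sizes are not given) yields 17 to 18. The step to 21 reproduces with the stated 12% attrition: 18/0.88 = 20.5. None of this gives a figure for abstinence, so it does not decide the present point.

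**Expected quitters per arm**, n × p. At 18 per arm: 18 × 0.047 = 0.85 and 18 × 0.06 = 1.08. At 21 per arm: 0.99 and 1.26.

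**Chance that nobody quits**, (1 − p)^(2n) with the same rate p in both arms:
- 4.7%: 0.953^36 = 17.7% (n = 18); 0.953^42 = 13.2% (n = 21).
- 6%: 0.94^36 = 10.8% (n = 18); 0.94^42 = 7.4% (n = 21).

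**Coverage of the 95% interval that goes with a two-group ANOVA.** The interval is d ± t × √(s² × 2/n), where d is the difference in proportions, s² = [n·p₁(1 − p₁) + n·p₂(1 − p₂)]/(2n − 2) with observed proportions, and t has 2n − 2 degrees of freedom. All pairs of binomial counts were enumerated. A table with no quitters was scored as a zero-width interval at zero. The last column leaves those tables out. All rates are assumptions.

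| Rates in the two arms | n per arm | Coverage, all tables | Coverage, no-quitter tables left out |
|---|---|---|---|
| 4.7% vs 4.7% | 18 / 21 | 0.993 / 0.989 | 0.991 / 0.987 |
| 6% vs 6% | 18 / 21 | 0.986 / 0.981 | 0.985 / 0.979 |
| 2% vs 10% | 18 / 21 | 0.845 / 0.881 | 0.944 / 0.949 |
| 5% vs 10% | 18 / 21 | 0.894 / 0.884 | 0.951 / 0.918 |
| 6% vs 12% | 18 / 21 | 0.893 / 0.915 | 0.923 / 0.932 |
| 5% vs 20% | 18 / 21 | 0.953 / 0.924 | 0.960 / 0.926 |
| 6% vs 20% | 18 / 21 | 0.939 / 0.938 | 0.944 / 0.940 |

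The no-quitter tables account for about half or more of the shortfall wherever low rates differ.

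**Type I error of the ANOVA**, same enumeration: 0.008 and 0.014 at 4.7% and 6% in both arms (n = 18); 0.011 and 0.020 (n = 21).

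**The choice of test matters.** For 4/21 versus 0/21: ANOVA p = 0.036, Barnard 0.044, Boschloo 0.056, Fisher 0.107.

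**The alternative interval.** Newcombe's interval is defined for every table. With nobody quitting, its limits are ± z²/(n + z²) = ± 3.84/21.84 = ± 0.176 (n = 18) or ± 3.84/24.84 = ± 0.155 (n = 21). Its coverage is 98% to 99% at 2% vs 10%, 5% vs 10% and 6% vs 12%. At n = 18 its mean width against that of the ANOVA interval is 0.404 against 0.263 at 5% vs 5% (54% wider) and 0.426 against 0.335 at 5% vs 10% (27% wider). At n = 21 the excess at 5% vs 10% is 24% (0.387 against 0.312).

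**The case against.** The strongest reply has five parts.

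1. *The ANOVA sentence may not be meant for abstinence.* Section 10 lists quantitative measures and side effects first, and abstinence appears only under Power Analysis. Hypothesis 2 also mentions parametric fits to relapse times, so ANOVA is not the only technique in the document. This reading is possible, but it leaves a primary outcome with no method at all, and the remedy is the same.

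2. *The quit rates are not the trial's.* This stands. The 4.7% and 6% describe stopping for at least three months and for more than a month in broad populations. The endpoint is abstinence after two weeks of treatment in treatment-seeking smokers. A reader might infer that the documents predict about 5%; they do not. If the active rate is 20% and the sham rate 6%, the chance that nobody quits is below 1% (0.6% at n = 18).

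3. *No confidence interval is planned.* This also stands. Section 10 speaks of significance tests, so the coverage figures concern an interval that would come with the ANOVA output.

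4. *Under-coverage and the uncomputable case are largely one event.* Mostly right, as the last column of the table shows. Some shortfall remains at 5% vs 10% with 21 per arm (0.918) and at 6% vs 12% (0.923 and 0.932).

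5. *If nobody quits, no test can show a difference.* True of the test. A score-type interval would still bound the difference, which the ANOVA cannot do.

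**Conclusion.** The concern holds in a limited form. A binary primary outcome falls under a rule prescribing ANOVA, and no binary method is given. If both arms quit at 4.7% to 6%, there is a 7% to 18% chance that the prescribed analysis cannot be computed. An interval attached to it covers about 98% to 99% at those equal rates and about 85% to 92% in the examples where low rates differ. These sizes rest on assumed quit rates and on 18 to 21 participants per arm.

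Stronger readings are not supported:
- *False positives are inflated.* At low rates the test is conservative (0.008 to 0.020 against 0.05).
- *The effect estimate is wrong.* The ANOVA estimate is the difference in observed proportions, the same risk difference that a binary analysis would report.
- *The intervals under-cover in general.* They over-cover at equal low rates, and coverage is 0.92 to 0.95 once the active rate is about 20% or more.
- *One arm without quitters defeats the ANOVA.* With a few quitters in the other arm it can still be computed; 4/21 versus 0/21 is an example.

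This should be corrected before analysis.

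**What to change.** In Section 10, limit ANOVA and mixed models to continuous outcomes. For abstinence at the end of treatment:
- define abstinence, state the assumed rate, analyse all randomised participants, and say how those with unknown status are counted;
- prespecify one named exact test, for example Boschloo, without leaving a choice between tests;
- report the risk difference with a Newcombe or score 95% confidence interval.

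The change touches analysis wording only; no visit, procedure or sample size is affected. It has a statistical price. In the scenarios 5% vs 5% and 5% vs 10% the intervals are about 24% to 54% wider than the ANOVA intervals. A borderline result can lose significance: 4/21 versus 0/21 gives p = 0.056 with Boschloo against 0.036 with ANOVA.

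The change restores validity, not power. As a guide, Fisher's exact test has 11% power (n = 18) or 16% (n = 21) at 6% vs 20%. With a 6% sham rate it needs an active rate of about 50% (n = 18) or 45% (n = 21) for 80% power. The plan should therefore present the abstinence comparison mainly as an estimate with its interval.
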